### 10.2.5 Visits 5 to 15 (Visits each 30 Days; V5 $\pm$ 3 days, V6 to V15 $\pm$ 7 days)

Subjects will continue to be monitored for safety and effectiveness at one-month intervals. On and after **Day 90**, subjects are eligible to exit the study once their GLS score at maximum frown has returned to Baseline (Investigator assessment). Subjects will return for monthly assessments until they reach their Baseline GLS score (Investigator assessment). Assessment procedures include:

- Brow Area Photography
- Effectiveness Evaluations Investigator (Blinded Evaluator)
  - GLS (max frown)
  - GAIS
- Effectiveness Evaluations Subject
  - GLS (max frown)
  - GAIS
  - Subject Satisfaction
  - Clinical Interview (Visit 5; Day 30 only) (Section 10.3.4)
- Safety Assessments Investigator (Blinded Evaluator)
  - Directed Questionnaire
  - Directed Review of Systems
  - Vital Signs
  - Physical Exam
  - Concomitant Medications
  - Adverse Events

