2. OVERVIEW OF STUDY DESIGN

2.1. Study Design

This is a multicenter, prospective, randomized, double-blind, active-controlled, single-treatment, increasing dose design.

Approximately 150 subjects will be randomized 1:1:1, to either 20U onabotulinumtoxinA, 20U prabotulinumtoxinA-xvfs, or 40U prabotulinumtoxinA-xvfs. Subjects with moderate or severe glabellar lines at maximum frown on the 4-point validated Glabellar Line Scale (*GLS*, 0=none, 1= mild, 2=moderate, 3=severe), as judged by the investigator and the subject, will be eligible.

Safety and effectiveness will be assessed on days 3, 7, and 30, then every 30 days up to 365 days or until the subject has returned to Baseline as assessed by the Investigator, at which point the subject will exit the study. Please refer to Table 1 below for visit specifics.

Duration of effect will be estimated by Kaplan-Meier analysis and will be based on the number of days from Treatment Day (Baseline) to the day that GLS severity (Investigator assessment) at maximum frown returns to the Baseline value (i.e., the treatment will be considered to remain effective for the amount of time during which GLS severity at maximum frown has not returned to Baseline severity).

The Evaluating Investigator (i.e., Blinded Investigator) will be responsible for managing the subject, monitor for related and unrelated adverse effects, and carrying out the evaluations. Injections of study drug will be performed by an "Unblinded Injector" (i.e., physician or nurse practitioner not responsible for subject follow-up).

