2.3. Primary Endpoint

The primary effectiveness endpoint will be duration of effect, defined as the number of days from Treatment Day (Baseline) to the day that GLS severity (Investigator assessment) at maximum frown returns to the Baseline value. The treatment will be considered to remain effective for the amount of time during which GLS severity at maximum frown has not returned to Baseline severity. Duration of effect will be estimated by Kaplan–Meier analysis.

Although the trial is not powered for inferential analysis, this will be the most influential outcome in the overall assessment of the effectiveness of prabotulinumtoxinA 40 Units, compared to prabotulinumtoxinA 20 Units, in treating moderate to severe glabellar lines.

Confidential Page 9/58

TABLE 1. SCHEDULE OF EVENTS AND PROCEDURES

Visit Number	V1 ¹ Screening	V2 ¹	V3	V4 (phone f/u)	V5 to V15 ²	V16 ³ (or Final Visit, or ET)	Unscheduled Visit 11
Day/Week/Month	≤ 14D	Tx Day	48Hr	D 7	D30 to D330 Monthly Visits	D365	
Visit Windows				±1 Day	D30 ±3D, ≥D60 ±7D	±14D	
Assessment and Procedures							
Informed Consent	X						
Inc/Excl Criteria	X						
Demographics, Med Hx	X						
Randomization to Study Tx 4		X					
Effectiveness - Investigator							
Glabellar Line Scale ⁵	X	X	X		X	X	X
Global Aesthetic Improvement			X		X	X	X
Effectiveness - Subject							
Glabellar Line Scale ⁵	X	X	X		X	X	X
7-Day Subject Diary		Х —		—			
Global Aesthetic Improvement			X		X	X	X
Subject Satisfaction Score			X		X	X	X
Clinical Interview 6					D30 only	X	X
Safety Evaluations							
Directed Questionnaire ⁷	X		X		X	X	X
Directed Review of Systems	X		X		X	X	X
Vital Signs 8	X		X		X	X	X
Physical Exam 9	X		X		X	X	X
UPT (as applicable)	X	X				X	
Clinical Laboratory Tests 10	X					X	X
ECG	X					X	X
Safety Assessment Phone Call				X			
Brow Area Photography	X	X	X		X	X	X
Concomitant Medications	X	X	X	X	X	X	X
AE Assessment		X	X	X	X	X	X

- 1. Screening and treatment visit can take place the same day, at the discretion of the investigator
- 2. Subjects will be followed monthly until their Glabellar Line Scale score is back to Baseline (Investigator assessment)
- 3. Subject exits study once their Glabellar Line Scale Score has returned to Baseline (Investigator assessment)
- 4. IP may be administered same day as Screening
- 5. Glabellar Line Scale at Maximum Frown, 0=none, 1=mild, 2=moderate, 3=severe
- 6. Clinical Interview Questions
 - What did you like about the treatment (clinically or other feedback)?

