7.2. Secondary Effectiveness Endpoints

Secondary effectiveness endpoints will be used to provide additional analyses regarding duration of effect of prabotulinumtoxinA 40U, prabotulinumtoxinA 20U, and onabotulinumtoxinA 20U. As duration of effect outcomes, secondary effectiveness endpoints will be assessed as described above for the primary endpoint. The mITT population will be used for summaries and comparisons. Secondary endpoints, in order of importance, will be:

- 1. Duration of effect (PraB vs. OnaB only, regardless of responder status), defined as the number of days from Treatment Day (Baseline) to the day that GLS severity (Investigator assessment) at maximum frown returns to the Baseline value.
- 2. Duration of effect (all treatment groups, regardless of responder status), defined as the number of days from Treatment Day (Baseline) to the day that GLS severity (subject assessment) at maximum frown returns to the Baseline value.
- 3. Duration of effect (all treatment groups) in GAIS responders (score of 2 or 1 at Day 30) as assessed by Investigator.
- 4. Duration of effect (all treatment groups) in GAIS responders (score of 2 or 1 at Day 30) as assessed by subject.
- 5. Duration of effect (all treatment groups) in SSS responders (score of 2 or 1 at Day 30) as assessed by subjects.

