7.7. General Considerations

Data will be listed by subject number. Data will be summarized by treatment and study visit, where applicable. For categorical parameters, the number and percentage of subjects/observations in each category will be presented; percentages will be based on the number of subjects in the relevant analysis population in each treatment group. For continuous parameters, descriptive statistics will include n (number of subjects or observations), mean, standard deviation, median, and range. A full description of the statistical methods planned for this study will be provided in the Statistical Analysis Plan (SAP). All programs for data output and analyses will be written in SAS version 9.4 or higher (SAS Institute, Inc., Cary, NC).

Missing Values: For the mITT analysis of primary, secondary, tertiary, and exploratory duration of effectiveness endpoints, in the case of a missed visit, subjects will be considered to have returned to Baseline if they are confirmed to have returned to Baseline at the next non-missed visit. Subjects will be considered to have to have returned to Baseline if they fail to attend 2 consecutive visits or drop out of the study. For missing observations for exploratory endpoints other than duration of effect data will be analyzed as observed without imputation.

Discontinuation and Drop-Outs: Dropouts will not be replaced. Subject disposition will summarize the number of subjects who were randomized and who discontinued from the study (including reasons for discontinuation).

Interim Analysis: An interim analysis will be conducted when >90% of subjects have completed Visit 8 (Day 120) to evaluate response to exposure (efficacy, duration) and adverse events. For assessment of the primary effectiveness endpoint, 95% CIs will be presented but statistical analyses will not be conducted and a statistical penalty for the final analysis will not be employed. While data by treatment group will be presented, individual subjects will not be unblinded.

Poolability of Investigative Sites: Data from all investigative sites will be pooled based on the assumption of clinical comparability: the same protocol will be used for all sites, all sites will be monitored for protocol compliance, and the same data collection instrument and methodology will be used across all sites.

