14.1 Subject Disposition

Table 14.1.1 Enrollment

Site	Screened	Screen Failures	Randomized	PP	ITT	SAFT
01	XX	XX	XX	XX	XX	XX
02	XX	XX	XX	XX	XX	xx
03	XX	XX	XX	XX	XX	XX
04	XX	XX	XX	XX	XX	xx
05	XX	XX	XX	XX	XX	XX
All sites	XX	XX	XX	XX	XX	XX

Number of subjects

Table 14.1.2 Subject Discontinuations with Primary Reason

Study Exit		PraB 40 (n = xx)	OnaB 20 (n = xx)	PraB 20 (n = xx)
Completion of Study	N	XX	XX	XX
	Completed up to return to BL	xx (xx.x%)	xx (xx.x%)	xx (xx.x%)
Primary Reason for d/c* prior	N	xx (xx.x%)	XX	XX
to return to BL	Adverse Event	xx (xx.x%)	xx (xx.x%)	xx (xx.x%)
	Lost to follow- up	xx (xx.x%)	xx (xx.x%)	xx(xx.x%)
	Withdrew consent	xx (xx.x%)	xx (xx.x%)	xx (xx.x%)
	Protocol violation	xx (xx.x%)	xx (xx.x%)	xx (xx.x%)
	Investigator Decision		xx (xx.x%)	xx (xx.x%)
	Other		xx (xx.x%)	xx (xx.x%)

Number of subjects (% in parenthesis). *d/c= discontinuation

Table 14.1.3 Listing of Subject Discontinuations

Subject	Treatment	Gender*	Age	Last Visit	Primary Reason for
Number	Group				Discontinuation
##-###	PraB 40	M/F	XX	V#	xxxxxxxxxxxxxxxx
##-###	PraB 20	M/F	XX	V#	xxxxxxxxxxxxxxx
##-###	OnaB 20	M/F	XX	V#	xxxxxxxxxxxxxxxx
##-###	OnaB 20	M/F	XX	V#	xxxxxxxxxxxxxxx
##-###	PraB 40	M/F	XX	V#	xxxxxxxxxxxxxxxx
##-###	PraB 20	M/F	XX	V#	xxxxxxxxxxxxxxx
##-###	PraB 40	M/F	XX	V#	XXXXXXXXXXXXXXXX
##-###	OnaB 20	M/F	XX	V#	XXXXXXXXXXXXXXXX

M=Male, F=Female

Version 1.1 31-May-2023 Confidential Page 24/58

Table 14.1.4 Subject Disposition per Visit

Disposition of Subjects at	PraB 40	OnaB 20	PraB 20
each Study Visit	(n = xx)	$(\mathbf{n} = \mathbf{x}\mathbf{x})$	$(\mathbf{n} = \mathbf{x}\mathbf{x})$
N	XX	XX	XX
V1 (screening)	xx (xx.x%)	xx(xx.x%)	xx(xx.x%)
V2 (pre-Tx)	xx(xx.x%)	xx(xx.x%)	xx (xx.x%)
V3 (48hr)	xx(xx.x%)	xx(xx.x%)	xx(xx.x%)
V4 (D7; phone f/u)	xx(xx.x%)	xx(xx.x%)	xx (xx.x%)
V5 (D30)	xx (xx.x%)	xx (xx.x%)	xx(xx.x%)
V6 (D60)	xx(xx.x%)	xx(xx.x%)	xx(xx.x%)
	xx(xx.x%)	xx(xx.x%)	xx (xx.x%)
	xx (xx.x%)	xx (xx.x%)	xx (xx.x%)
V16 (D365)	xx (xx.x%)	xx (xx.x%)	xx (xx.x%)

Number of subjects (% in parenthesis)

Table 14.1.5 Study Dates

FPFV	LPFV	LPLV	Enrollment Duration	Study Duration
dd-mmm-yyyy	dd-mmm-yyyy	dd-mmm-yyyy	XXX	XXX

FPFV= First Patient First Visit, LPFV= Last Patient First Visit, LPLV= Last Patient Last Visit. Enrollment duration=FPFV-LPFV+1, Study duration=FPFV-LPLV+1

Confidential Page 25/58

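### Follow-up ends on the Investigator's GLS alone, so secondary durations 2 to 5, which depend on other ratings, are informatively censored at exit, and the SAP has no rule for it

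*SAP*

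**What the plan says.** **Endpoints.** Secondary 2 in SAP 7.2 runs from treatment "to the day that GLS severity (subject assessment) at maximum frown returns to the Baseline value". Secondary 5 is "Duration of effect (all treatment groups) in SSS responders (score of 2 or 1 at Day 30) as assessed by subjects"; secondaries 3 and 4 are the same on GAIS, rated by Investigator and by subject. Section 7.2 does not say what ends the duration for 3 to 5. The shells for Tables 14.3.2.3 to 14.3.2.5 do: that scale's own score returns to Baseline. For the method, "secondary effectiveness endpoints will be assessed as described above for the primary endpoint", which means the Kaplan-Meier medians and Cox model of 7.1.

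**Exit.** SAP 2.1 follows subjects up to Day 365 or "until the subject has returned to Baseline as assessed by the Investigator, at which point the subject will exit the study". SAP Table 1 (footnotes 2 and 3) and Protocol 4.1 and 10.2.6 say the same. Protocol 10.2.5 alone makes exit possible only from Day 90. Protocol 4.1 allows glabellar treatment after exit, so later ratings could not be used.

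**Missing data.** SAP 7.7 counts subjects as returned to Baseline "if they fail to attend 2 consecutive visits or drop out of the study". In the shell for SAP Table 14.1.2, the exit in question appears under completion, as "Completed up to return to BL", separate from discontinuations before return.

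No text says what happens to a subject who exits on the Investigator's GLS while another rating is still improved, and no sensitivity analysis addresses it.

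**The concern.** Secondaries 2 to 5 each need one rating to return, while observation stops when a different rating does. The same holds for the subject-rated durations in SAP 7.3. A subject who still reports benefit at the exit visit leaves an incomplete duration, and leaves because the Investigator sees the effect as gone. If censored, that subject is represented afterwards by subjects whose Investigator rating has not returned, who probably have longer effects. If set to an event, the result is no longer the stated endpoint. Duration is what this trial sets out to describe, so the medians and curves in these tables are what a reader would carry away.

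**Working it through.** **1. The plan's own figure.** The plan gives no figure for this point. Its power statement (SAP 7.6) supplies a reference median of 4 months and a hazard ratio of 0.47. To reproduce it I assume 12 months of follow-up, which that paragraph does not state.

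- Rates per month: reference ln2/4 = 0.1733; 40U 0.47 × 0.1733 = 0.0814; censoring −ln(0.9)/12 = 0.0088.
- Expected events per arm: 50 × λ/(λ+c) × (1 − exp(−12(λ+c))) = 42.2 and 29.8, total 72.1 before rounding.
- Schoenfeld: √72.1/2 × |ln 0.47| − 1.96 = 1.25, power 0.89. Freedman: √72.1 × 0.53/1.47 − 1.96 = 1.10, power 0.86.

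The stated 80% is therefore not reproduced. The gap is conservative and has no bearing here; only the median and hazard ratio are carried forward.

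**2. Which endpoints are cut short.**

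| Duration | Rating that must return | Same as exit trigger? |
|---|---|---|
| Primary; secondary 1 | Investigator GLS | Yes, unaffected |
| Secondary 2 | Subject GLS | No |
| Secondary 3 | Investigator GAIS | No |
| Secondary 4 | Subject GAIS | No |
| Secondary 5 | SSS | No |
| SAP 7.3, subject-rated durations | Subject GLS | No |

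Subjects whose own rating returns at or before the exit visit are observed correctly.

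**3. Censored or event?** Protocol 11.3 equates withdrawal with dropout and lists the reasons; return to Baseline on the Investigator's GLS is not among them. The shell for Table 14.1.2 counts this exit as completion. Together they point to censoring, though the SAP never says so.

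**4. Size.** Assumptions not in the documents: subject reference median 120 or 150 days, and correlation between the two ratings. Investigator reference median is 120 days and the hazard ratio 0.47 on both ratings. Times are linked by a Gaussian copula and observed at visits every 30 days to Day 330, then Day 365. Exit is at the Investigator's return, not before Day 90. There are 200,000 subjects per arm. Day 180 survival with exponential times:

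| Correlation | Subject median | Arm | Cut off at exit | Full follow-up | Censored at exit | Event at exit |
|---|---|---|---|---|---|---|
| 0.6 | 120 | Reference | 31.8% | 0.354 | 0.406 | 0.216 |
| 0.6 | 120 | 40U | 30.0% | 0.615 | 0.651 | 0.472 |
| 0.8 | 120 | Reference | 27.7% | 0.354 | 0.418 | 0.258 |
| 0.8 | 120 | 40U | 25.8% | 0.612 | 0.660 | 0.514 |
| 0.6 | 150 | Reference | 39.5% | 0.435 | 0.496 | 0.248 |
| 0.6 | 150 | 40U | 34.6% | 0.677 | 0.714 | 0.506 |
| 0.8 | 150 | Reference | 37.4% | 0.435 | 0.517 | 0.290 |
| 0.8 | 150 | 40U | 32.0% | 0.679 | 0.731 | 0.548 |

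- Median, 40U, first case (correlation 0.6, subject median 120): 270 days with full follow-up, 330 censored, 180 with exit as event.
- Wider range (correlation 0.3 to 0.8, Weibull shape 1 to 2): about 26% to 59% of an arm is cut off, depending partly on whether a Day 365 exit counts. Censoring overstates Day 180 survival by about 2 to 15 points. Event-at-exit understates it by about 7 to 29 points and is the worse of the two in 23 of 24 arm-by-scenario cells.
- Correlation 0, subject median 120, reference arm: censored 0.353 against 0.354 true. The bias comes from the correlation.

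**5. Hazard ratio.** With equal effects on both ratings (first case): full 0.489, censored 0.495, event 0.522. Both alternatives lie on the same side of the full-follow-up value. If the subject rating has no treatment effect (true 1.00) and the Investigator rating has 0.47, censoring gives 1.03 to 1.18 and event-at-exit 0.81 to 0.89 (correlation 0.3 to 0.9).

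**The case against.** These are secondary analyses in a trial that both documents call unpowered, with results for interpretation only (SAP 1.3 and 7.6). The hazard ratio hardly moves in the equal-effect case. The shells already show event and censored counts per arm, and subject ratings are tabulated by visit. The size depends on a correlation and subject medians that the documents do not give.

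Most of this stands and limits the weight of the point. It does not remove it. A descriptive trial rests on its medians and curves, which are what shift. The censored row pools Investigator-triggered exits with subjects still improved at Day 365, so the reader cannot see how many durations were cut short.

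A reader might infer that the dropout rule in SAP 7.7 turns every such exit into a false event. The documents do not support that: Protocol 11.3 and Table 14.1.2 class the exit otherwise. A reader might also infer that counting exit as an event is the safer main analysis. Step 4 shows that it usually distorts the curve more, and step 5 that it carries the Investigator's treatment effect into a subject-rated endpoint.

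**Conclusion.** The concern holds for secondaries 2 to 5 and the subject-rated exploratory durations. The exit is most naturally censored. That censoring is informative if the ratings correlate positively, which is to be expected because they judge the same lines. Curves and medians then overstate duration.

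The direction follows from the plan's rules plus positive correlation. The size, about 2 to 15 points at Day 180, rests on the assumptions in step 4 and vanishes at zero correlation.

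It would go too far to infer that the primary result is biased: its event is the exit criterion itself. Nor does the check show a distorted treatment comparison in general. With equal effects on both ratings the hazard ratio barely changes; it shifts more only if the effects differ.

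**What to change.** In SAP 7.2 and 7.7, state that Investigator-determined exit is not a dropout and is not covered by the dropout-equals-event rule. For each affected duration:

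- Keep censoring at exit as the main version, described as likely an upper limit for the curve under positive correlation.
- Beside it, show time to the first of own-rating return or Investigator exit. Label it a composite and a lower limit for the curve, since it can never exceed the own-rating time. Do not make it the main analysis.
- Do not present the two as bounds on the hazard ratio.
- Report per arm how many subjects were still improved on that rating at exit, separately from Day 365 censoring. Do not quote the censored medians without these additions.

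The Day 90 condition in Protocol 10.2.5 and the unconditional exit in Protocol 4.1 and SAP 2.1 must also be reconciled, because they decide when truncation can start.

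The cost is SAP wording, one extra run per table, and wider stated uncertainty on the secondary durations. No new visits or data are needed.

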7.3. Exploratory Effectiveness Endpoints

Exploratory effectiveness endpoints will be evaluated for signals of effectiveness to explore whether any should be elevated in importance for subsequent trials. These endpoints will be assessed using either logistic regression (for binary endpoints) or survival analysis-type methods as described above. Comparisons will be made between all treatment groups. Chi-square tests of association or Fisher's exact tests will be used to compare treatment group differences in proportion of subjects returning to Baseline at each time point in the study. Exploratory endpoints will be:

Version 1.1 31-May-2023 Confidential Page 18/58

- 1. Duration of effect for GLS responders, defined as the number of days from Treatment Day (Baseline) to the day that GLS severity at maximum frown returns to the Baseline value. Analyses will be conducted for Investigator and subject assessments of GLS. Various responder definitions will be tested (1-Point, 2-Point and 3-Point responders at any time during the study; GLS Score of 0 or 1 at any time during the study; 1-Point responders at Day 30).
- 2. Time to loss of GLS responder status, with responder being defined as a GLS score of 0 or 1 at any point during the study. Analyses will be conducted for Investigator and subject assessments of GLS.
- 3. GLS responder rates (Investigator assessments) at each study visit. Various responder definitions will be tested (1-Point, 2-Point and 3-Point responders; GLS Score of 0 or 1; GLS Score 0 or 1 & ≥2-Point improvement; GLS Score 0 or 1 & ≥2-Point improvement & Investigator GLS = subject GLS).
- 4. GLS responder rates (Subject assessments) at each study visit. Various responder definitions will be tested (1-Point, 2-Point and 3-Point responders; GLS Score of 0 or 1).
- 5. GAIS response (score of 2 or 1) as assessed by Investigator and subject at each visit.
- 6. SSS response (score of 2 or 1) as assessed by subjects at each visit.
- 7. Onset of effect as assessed by subjects through the 7-Day Subject Diary.

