#### **Phase III European Clinical Trial for Glabellar Lines**

The EVB-003 study was the third Phase III safety and efficacy study in the prabotulinumtoxinA clinical development program and was conducted in Europe and Canada (REF 3). 540 subjects with moderate to severe glabellar lines, or a GLS score of 2 or 3, as assessed by the investigator at maximum frown, were eligible to be enrolled provided that subjects also felt their glabellar lines had an important psychological impact, such as on their mood, anxiety, or depressive symptoms. On Day 0, eligible subjects were randomly assigned in a 5:5:1 ratio to receive a single treatment of 20 units of prabotulinumtoxinA, 20 units of onabotulinumtoxinA or placebo.

The primary efficacy endpoint was defined as the proportion of subjects classified as responders on Day 30. A responder was a subject with a GLS score of 0 or 1, as assessed by the investigator at maximum frown. The primary analysis of the primary efficacy endpoint in the EVB-003 study showed prabotulinumtoxinA's superiority over placebo, and established prabotulinumtoxinA's non-inferiority to BOTOX. The percentages of responders for the primary efficacy endpoint were:

- 4.2% in the placebo group, 95% CI (0.0, 9.8);
- 82.8% in the onabotulinumtoxinA group, 95% CI (78.1, 87.5); and
- 87.2% in the prabotulinumtoxinA group, 95% CI (83.0, 91.5).

The absolute differences between the treatment groups were:

- 83.1% between prabotulinumtoxinA and placebo groups, 95% CI (70.3, 89.4), (p<0.001), indicating prabotulinumtoxinA was superior to placebo; and
- 4.4% between prabotulinumtoxinA and onabotulinumtoxinA groups, 95% CI (-1.9, 10.8), with non-inferiority of prabotulinumtoxinA versus onabotulinumtoxinA concluded based on the lower bound of the 95% CI for the absolute difference exceeding -10.0%.

As presented in the table below, within each group, 32.7% of placebo subjects, 41.9% of onabotulinumtoxinA subjects and 37.6% of prabotulinumtoxinA subjects experienced AEs. One placebo subject (1/49, 2.0%), one onabotulinumtoxinA subject (1/246, 0.4%) and three prabotulinumtoxinA subjects (3/245, 1.2%) experienced a total of 11 SAEs and none were assessed as study drug related. The eyelid ptosis rates were 1.6% in the prabotulinumtoxinA arm and 0% in the onabotulinumtoxinA arm and the eyebrow ptosis rates were 0% in the prabotulinumtoxinA arm and 0.4% in the onabotulinumtoxinA arm.

evolus™ evolus-cl	IN201 Version 2.0 23-Nov-2022	Confidential Page 19/68

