#### 5.1 Inclusion Criteria

A subject must meet the following key criteria in order to be eligible for enrollment in the study:

- 1. Outpatient, male or female of any race, 18 years of age or older.
- 2. Female subjects of childbearing potential must have a negative UPT during Visit 1 (Screening), Visit 2 (if applicable) and practice a reliable method of contraception for the duration of the study.

A female is considered of childbearing potential unless she is:

- postmenopausal for  $\geq 12$  months prior to study treatment administration;
- without a uterus and/or both ovaries; or
- has been surgically sterile for  $\geq 6$  months prior to study treatment administration.

Reliable methods of contraception are:

- hormonal methods (contraceptive pill or implant) or IUD in use  $\geq 90$  days prior to enrolment;
- barrier methods (e.g., diaphragm w/ spermicide or condom w/ spermicide in use  $\geq 14$  days prior to study treatment administration; or
- partner vasectomized  $\geq 3$  months (or confirmed '0' sperm count) prior to enrolment.

[Exception: Females of childbearing potential who are not sexually active are not required to practice a reliable method of contraception. These subjects may be enrolled at Investigator's discretion if they are counseled to remain sexually inactive during the study or agree to use an approved method of contraception should they become sexually active and understand the possible risks in getting pregnant during the study.]

- 3. Moderate to severe glabellar lines (i.e., score of 2 or 3) on maximum frown as assessed by the investigator using the GLS.
- 4. Subject has moderate to severe glabellar lines (i.e., score of 2 or 3) at maximum frown as assessed by the subject using the GLS.
- 5. Able to follow study instructions and likely to complete all required visits.
- 6. Sign the IRB-approved ICF prior to any study-related procedures being performed.

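### The per-visit responder odds ratios have no rule for an arm at 0% or 100%, where ordinary logistic regression gives no finite estimate

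*SAP*

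**What the plan says.** SAP 7.3 covers all binary exploratory endpoints in one sentence: "These endpoints will be assessed using either logistic regression (for binary endpoints) or survival analysis-type methods as described above". The endpoints include "GLS responder rates (Investigator assessments) at each study visit", the matching subject-assessed rates, and GAIS and SSS response by visit. The same section adds: "Chi-square tests of association or Fisher's exact tests will be used to compare treatment group differences in proportion of subjects returning to Baseline".

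The shells (SAP Tables 14.3.3.3.1 to 14.3.3.5.1) show three results for each pair of arms within each visit and definition: a p-value on the percentage row, then an OR with 95% CI, then a separate OR p-value.

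SAP 7.7 names the software ("All programs for data output and analyses will be written in SAS version 9.4 or higher") and the missing-data rule ("For missing observations for exploratory endpoints other than duration of effect data will be analyzed as observed without imputation"). Neither section mentions empty cells, separation, penalised or exact logistic regression, the test behind the OR p-value, or the interval method for the single percentages. SAP 7.4.1 does name Wilson intervals, but only for the overall incidence of AEs and SAEs.

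**The concern.** If every subject, or no subject, in one arm responds, logistic regression fitted by ordinary maximum likelihood has no finite treatment coefficient. The OR runs off to zero or infinity, the Wald interval becomes useless, and the Wald p-value approaches 1. Covariates in the model would not cure this, because treatment arm alone still predicts the outcome perfectly in that arm.

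Some planned cells invite this:
- **≥3-point improvement.** Entry requires "Moderate to severe glabellar lines (i.e., score of 2 or 3) on maximum frown as assessed by the investigator using the GLS", so a subject starting at 2 cannot reach it.
- **The 48-hour visit**, the earliest post-treatment assessment.
- **≥1-point response at Day 30**, where response may be near total.
- **Late visits.** Under Protocol 10.2.5, from Day 90 "subjects are eligible to exit the study once their GLS score at maximum frown has" returned to its starting value, and the analysis is as observed, so denominators shrink.

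The exploratory endpoints are meant to show which outcomes deserve a higher place in later trials. An undefined OR with a p-value near 1 could obscure such a signal. A remedy chosen after unblinding would not be pre-specified.

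**Working it through.** The plan gives no figure of its own on this point, so the check uses an illustrative table and then asks how often such tables would arise.

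**Inputs.** 50 per arm (SAP 7.6). GLS 0 or 1 at Day 30 in 87.2% on prabotulinumtoxinA 20U in EVB-003 (Protocol 1.1). A 2-point composite responder rate of 4.6% at Day 150 on 20U in EV-001 and EV-002 (Protocol 1.1), used only as a proxy for a low rate. All other rates are assumptions.

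**1. The illustrative table, 50/50 against 44/50** (equivalent to 0/50 against 6/50).

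- *Fisher.* One-sided p = C(50,6)/C(100,6) = 0.0133; two-sided p = 0.027.
- *Maximum likelihood.* The log-likelihood is 44·ln(p0) + 6·ln(1 − p0) + 50·ln(p1). It keeps rising as p1 approaches 1, so the log OR has no finite maximum. In a Newton fit the estimate grows by about 1 per iteration, while its standard error grows about 1.65-fold:

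| Iteration | log OR | SE | Wald p |
|---|---|---|---|
| 11 | 10.21 | 63.1 | 0.87 |
| 15 | 14.21 | 466.6 | 0.976 |
| 19 | 18.21 | 3447.6 | 0.996 |

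 The printed p-value therefore depends on the stopping rule, not on the data.
- *Likelihood ratio.* The maximised log-likelihood is minus 22.70 with one common rate and minus 18.35 with a rate per arm. Twice the difference of 4.35 is 8.70 on 1 df, p = 0.003. This p-value is usable, but the OR beside it is still infinite.
- *Firth.* In a 2×2 table this amounts to adding one half to each cell: the odds are 50.5/0.5 = 101 in one arm and 44.5/6.5 = 6.846 in the other, and their ratio is 14.8. The profile CI is 1.67 to 1944 and the penalised likelihood-ratio p is 0.011.
- *Exact conditional.* Median-unbiased OR 9.0, lower 95% limit 1.25, upper limit infinite, p = 0.027.

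**2. Sensitivity of the example.** Against 50/50, Fisher p is 0.056 for 45/50 and 0.117 for 46/50. So 44/50 is the first table to cross 0.05.

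**3. How often a cell is empty.** P(at least one of two arms at 50/50) = 1 − (1 − pA^50)(1 − pB^50). For the conflict with Fisher p < 0.05, the other arm must have 44 or fewer responders: pA^50 × P(≤44 of 50 in B), plus the same with the arms exchanged.

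| True rates | Empty cell | Empty cell and Fisher p < 0.05 |
|---|---|---|
| 95% and 95% | 15% | 2 × 0.077 × 0.038 = 0.6% |
| 98% and 98% | 60% | 0.03% |
| 99% and 99% | 84% | 0.001% |
| 90% and 97% | 22% | 0.218 × 0.384 = 8% |
| 87.2% and 98% | 36% | 0.364 × 0.63 = 23% |

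At 87.2% in both arms an empty cell has probability 1 − (1 − 0.872^50)² = 0.2%, so GLS 0 or 1 at Day 30 is rarely affected. From a starting score of 2 or 3, a score of 0 or 1 is already at least a 1-point gain, so the ≥1-point rate can only be higher. How much higher is not documented.

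At the low end, 0/50 at 4.6% has probability 0.954^50 = 9.5%. Together with at least 6/50 in the other arm, the probability is 0.095 × 0.384 = 3.6% if that arm's rate is 10%, and 0.095 × 0.952 = 9.0% if it is 20%.

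**4. Late visits.** Under the plan's exponential 4-month median, and ignoring censoring, 50 × 0.5^(9/4) = 10.5 reference subjects have not returned to their starting score at month 9. Empty cells are easier to reach with denominators of that size.

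**5. Single percentages.** At 50/50 the Wilson interval has lower limit n/(n + z²) with n = 50 and z = 1.96, which gives 92.9% to 100% and is informative at the boundary.

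**The case against.** The strongest reply is that the failing method is partly inferred. The SAP says logistic regression; it does not say Wald, and a likelihood-ratio p on the same table would be 0.003. That stands for the p-value. It does not rescue the OR and its interval, which the shells require and which have no finite maximum-likelihood value.

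A reader might also infer that a Fisher p-value of 0.03 is planned beside a Wald p-value near 1. The documents do not say so. SAP 7.3 attaches the chi-square or Fisher test to return to the starting score, not to each responder rate. Placing it on the percentage row is a reasonable reading of the shells, since the ≥1-point rate is essentially the complement, but it is a reading. If it is right, each block already carries a valid test and both percentages, and the reader is not left without evidence.

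Three further inferences do not hold:
- The 15% to 84% chances of an empty cell are not chances of missing a signal. They assume equal true rates that no section gives, so there is no difference to miss, and the conflict with Fisher becomes rarer as they rise.
- The shells plan 13 definitions × 13 visits × 3 pairs = 507 ORs. That counts every cell, not those at risk.
- SAP 7.3 does not make these endpoints decide what is elevated. They are screened for signals, with no p-value rule, and SAP 1.3 treats the analyses as interpretive.

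**Conclusion.** The point holds as a gap in the exploratory analysis. With an empty cell, the planned OR and interval do not exist under ordinary maximum likelihood, and a Wald p-value would be close to 1 even for a table where Fisher gives 0.027.

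The exposure is confined to sparse cells: chiefly ≥3-point response, the 48-hour visit, ≥1-point response at Day 30, and thin late visits. Its frequency cannot be fixed from the documents. The chance of a misleading cell runs from well under 1% when the arms share a high rate to about 23% at 87.2% against 98%, and all but the 87.2% is assumed. These figures also assume 50 observed subjects per arm. Where both arms are empty at the same end, Fisher p is 1 and nothing is lost.

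The primary and secondary results are untouched. This is a cheap improvement, not a flaw in the trial's main inference.

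**What to change.** Add to SAP 7.3:

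1. Whenever a cell of the treatment-by-response table is empty, the per-visit OR comes from Firth-penalised logistic regression with a profile-likelihood 95% CI and penalised likelihood-ratio p-value (or from exact logistic regression with its exact CI and p-value).
2. The p-value on the percentage row is Fisher's exact test.
3. Intervals for single proportions are Wilson intervals, as already planned for AEs and SAEs.

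A risk difference with a Newcombe interval could be shown alongside, but that is an optional addition.

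The cost is a few sentences in the SAP and an option in the SAS code. The downside is slight shrinkage of the OR in sparse cells. Intervals there will stay wide, as 1.67 to 1944 shows, which is a fair picture of what such a table can support.
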